**Glomerular Filtration Rate (Cohorts 2 through 4):**

Measured GFR determined using the FAST VFI Technology will be compared to the mGFR determined using the Iohexol clearance test. The results will be listed by subject and summarized by presenting descriptive statistics for each cohort. Correlation analysis and Bland-Altman plots will be used to compare the FAST mGFR with Iohexol clearance. Subjects in Cohort 1 will not receive Iohexol and will not contribute to the overall PD statistical analysis.

Estimated GFR calculated using primarily the CKD-Epi equation in addition to the MDRD, and Cockcroft-Gault equations will be listed by subject and summarized by presenting descriptive statistics for each cohort.

**Safety Analysis:**

12-lead ECG, vital signs, pulse oximetry, and clinical laboratory test data (observed and change from baseline) will be summarized by cohort, time point, and treatment using appropriate descriptive statistics. Physical examination findings will be listed only.

The number and percentage of subjects reporting any treatment-emergent AE (TEAE) will be tabulated by system organ class and preferred term, cohort, and treatment (coded using Medical Dictionary for Regulatory Activities). Treatment-emergent AEs will be further classified by severity and relationship to treatment.

---

CONFIDENTIAL

**Table 2.1 Schedule of Assessments and Procedures – Cohort 1 (Single-dose Administration of VFI)**

Study Procedure	Screening	Admission a	Treatment Period													Discharge	EOS b	
Study Day	-21 to -2	-1	1													2	21 (± 1)	
Nominal Time Relative to Start of VFI Bolus Injection	-	-	Pre	0 m	15 m	30 m	60 m	120 m	130 m	165 m	195 m	205 m	310 m	370 m	480 m	12 h	24 h	480 h
Informed consent	X																	
Inclusion/exclusion criteria	X	X																
Demographics	X																	
Height	X																	
Body weight	X	X															X	
BMI c	X	X																
Medical and surgical history	X	X d																
Physical examination	X	X														X	X	
Vital signs and pulse oximetry e	X	X	X	X	X	X	X	X	X	X	X	X	X	X	X	X	X	
12-lead ECG e	X	X	X		X											X		
Clinical laboratory tests f	X	X													X g		X	X
Renal function assessment h	X	X																
Urine protein to creatinine ratio i			X													X		
Serology (HIV, HBsAg, HCV)	X																	
FSH (females only)	X																	
Pregnancy Test (females only)	X	X																

CONFIDENTIAL

**Table 2.1 Schedule of Assessments and Procedures – Cohort 1 (Single-dose Administration of VFI)**

Study Procedure	Screening	Admission a	Treatment Period												Discharge	EOS b		
Study Day	-21 to -2	-1	1												2	21 (± 1)		
Nominal Time Relative to Start of VFI Bolus Injection	-	-	Pre	0 m	15 m	30 m	60 m	120 m	130 m	165 m	195 m	205 m	310 m	370 m	480 m	12 h	24 h	480 h
Urine drugs of abuse and serum alcohol screen	X	X																
In-house residency		X	X	X	X	X	X	X	X	X	X	X	X	X	X			
FAST VFI administration				X														
5% Albumin Infusion										X								
FD001 and FD003 PK/PD plasma and urine samples			Refer to Table 2.4 for the PK and PD sampling schedule.															
AEs				X	X	X	X	X	X	X	X	X	X	X	X	X	X	
SAEs	X	X	X	X	X	X	X	X	X	X	X	X	X	X	X	X	X	
Concomitant medications	X	X	X	X	X	X	X	X	X	X	X	X	X	X	X	X	X	

Abbreviations: BMI = body mass index; ECG = electrocardiogram; EOS = end-of-study; FSH = follicle-stimulating hormone; h = hours; HBsAg = hepatitis B surface antigen; HCV = hepatitis C virus; HIV = human immunodeficiency virus; m = minutes; PD = pharmacodynamic; PK = pharmacokinetic; Pre = predose; VFI = visible fluorescent injectate

- Assessments conducted upon clinical research unit admission will be used to reconfirm a subject's eligibility for enrollment into the study.
- Subjects who terminate from the study early will have EOS procedures performed at the time of discontinuation.
- BMI will be calculated using the height obtained at screening.
- Interim medical and surgical history will be collected to determine if any changes have occurred since screening.
- Vital signs and ECGs will be measured after the subject has been resting quietly in a supine position or in the most recumbent position possible for at least 5 minutes.
- Refer to Table 8.3 for a detailed list of clinical laboratory test parameters.
- Hematology and serum chemistry only. Glucose and total cholesterol measurements will not be reported at 480 minutes as the subject will not have been fasting for 8 hours prior.
- Measurement of serum blood urea nitrogen, serum creatinine, and calculation of estimated glomerular filtration rate (eGFR) using the Modification of Diet in Renal Disease (MDRD), Chronic Kidney Disease Epidemiology Collaboration (CKD-EPI; 2009), and Cockcroft-Gault equations.
- Subjects should be fasting prior to urine protein to creatinine ratio measurement.

CONFIDENTIAL

FAST BioMedical  
Protocol Number: 36770001  
Final Protocol 1.1

NOTE: In the event that multiple postdose procedures are required to be conducted at the same nominal time point, the timing of PD blood sample collections will take priority over all other scheduled activities except for dosing. In practice, the following order is recommended: (1) ECG recording; (2) vital signs assessments; (3) PD blood sampling; (4) clinical laboratory tests sampling; (5) physical examination. Electrocardiograms and vital signs may be conducted up to 15 and 10 minutes, respectively, prior to the nominal time to minimize the potential autonomic effects of blood draws on these measurements.

CONFIDENTIAL

**Table 2.2 Schedule of Assessments and Procedures – Cohort 2 (Repeat-dose Administration of VFI)**

Study Procedure	Screening	Admission a	Treatment Period													Discharge	Follow-up			EOS b	
Study Day	-21 to -2	-1	1 and 2													3	5 (± 1)	9 (± 1)	16 (± 1)	22 (± 1)	
Nominal Time Relative to Start of VFI Bolus Injection	-	-	Pre	0 m	15 m	30 m	60 m	120 m	160 m	170 m	280 m	310 m	340 m	370 m	480 m	12 h	24	72 h	168 h	336 h	480 h
Informed consent	X																				
Inclusion/exclusion criteria	X	X																			
Demographics	X																				
Height	X																				
Body weight	X	X																	X		
BMI c	X	X																			
Medical and surgical history	X	X d																			
Physical examination	X	X														X			X		
Vital signs and pulse oximetry e	X	X	X	X	X	X	X		X	X	X	X	X	X	X	X	X	X	X		
12-lead ECG f	X	X	X		X											X					
Clinical laboratory tests g	X	X													X g		X	X g	X g	X	
Renal function assessment h	X	X																			
Urine protein to creatinine ratio i			X													X					
Serology (HIV, HBsAg, HCV)	X																				
FSH (females only)	X																				
Pregnancy Test (females only)	X	X																			

CONFIDENTIAL

**Table 2.2 Schedule of Assessments and Procedures – Cohort 2 (Repeat-dose Administration of VFI)**

Study Procedure	Screening	Admission a	Treatment Period														Discharge	Follow-up			EOS b
Study Day	-21 to -2	-1	1 and 2														3	5 (± 1)	9 (± 1)	16 (± 1)	22 (± 1)
Nominal Time Relative to Start of VFI Bolus Injection	-	-	Pre	0 m	15 m	30 m	60 m	120 m	160 m	170 m	280 m	310 m	340 m	370 m	480 m	12 h	24	72 h	168 h	336 h	480 h
Urine drugs of abuse and serum alcohol screen	X	X																			
In-house residency		X	X	X	X	X	X	X	X	X	X	X	X	X	X	X					
FAST VFI administration j				X													X				
Iohexol administration k									X												
FD001 and FD003 PK/PD plasma and urine samples																	Refer to Table 2.5 for the PK and PD sampling schedule.				
Iohexol PD plasma samples																	Refer to Table 2.5 for the PK and PD sampling schedule.				
AEs				X	X	X	X	X	X	X	X	X	X	X	X	X	X	X	X	X	
SAEs	X	X	X	X	X	X	X	X	X	X	X	X	X	X	X	X	X	X	X	X	
Concomitant medications	X	X	X	X	X	X	X	X	X	X	X	X	X	X	X	X	X	X	X	X	

Abbreviations: BMI = body mass index; ECG = electrocardiogram; EOS = end-of-study; FSH = follicle-stimulating hormone; h = hours; HBsAg = hepatitis B surface antigen; HCV = hepatitis C virus; HIV = human immunodeficiency virus; m = minutes; PD = pharmacodynamic; PK = pharmacokinetic; Pre = predose; VFI = visible fluorescent injectate

- Assessments conducted upon clinical research unit admission will be used to reconfirm a subject's eligibility for enrollment into the study.
- Subjects who terminate from the study early will have EOS procedures performed at the time of discontinuation.
- BMI will be calculated using the height obtained at screening.
- Interim medical and surgical history will be collected to determine if any changes have occurred since screening.
- Vital signs and ECGs will be measured after the subject has been resting quietly in a supine position or in the most recumbent position possible for at least 5 minutes.
- Refer to [Table 8.3](#) for a detailed list of clinical laboratory test parameters.

CONFIDENTIAL

- g. Hematology and serum chemistry only. Glucose and total cholesterol measurements will not be reported at 480 minutes as the subject will not have been fasting for 8 hours prior.
- h. Measurement of serum blood urea nitrogen, serum creatinine, and calculation of estimated glomerular filtration rate (eGFR) using the Modification of Diet in Renal Disease (MDRD), Chronic Kidney Disease Epidemiology Collaboration (CKD-EPI; 2009), and Cockcroft-Gault equations.
- i. Subjects should be fasting prior urine protein to creatinine ratio measurement. The 24-hour measurement on Day 2 will also act as the predose measurement for VFI dose 2. An additional ratio will be calculated 24 hours post VFI dose 2.
- j. VFI administration on Day 2 will occur 24 hours following VFI administration on Day 1.
- k. Iohexol administration will only occur on Day 1.

NOTE: In the event that multiple postdose procedures are required to be conducted at the same nominal time point, the timing of PK and PD blood sample collections will take priority over all other scheduled activities except for dosing. In practice, the following order is recommended: (1) ECG recording; (2) vital signs assessments; (3) PK and PD blood sampling; (4) clinical laboratory tests sampling; (5) physical examination. Electrocardiograms and vital signs may be conducted up to 15 and 10 minutes, respectively, prior to the nominal time to minimize the potential autonomic effects of blood draws on these measurements.

CONFIDENTIAL

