**Table 5.1      Planned Dose Cohorts**

Cohort	eGFR	VFI Dose	Number of Doses	Comparator Dose	Number of Doses	Number of Subjects
1*	≥ 60 mL/min/1.73 m 	47 mg/3 mL	1	---	---	Up to 8
2	≥ 60 mL/min/1.73 m 	47 mg/3 mL	2	Iohexol 5 mL	1	Up to 8
3	≥ 30 and < 60 mL/min/1.73 m 	47 mg/3 mL	1	Iohexol 5 mL	1	Up to 8
4	≥ 15 and < 30 mL/min/1.73 m 	47 mg/3 mL	1	Iohexol 5 mL	1	Up to 8

\*Subjects in Cohort 1 will receive a volume challenge

Cohort 1:

Eligible subjects ≥ 50 kg in weight will receive a single dose of VFI followed 130 minutes later by a 350 mL infusion of 5% albumin over 30 minutes on Day 1. Eligible subjects < 50 kg in weight will receive a single dose of VFI followed 130 minutes later by a maximum infusion of 5% albumin of 7 mL/kg over 30 minutes on Day 1. Subjects will remain resident in the CRU for at least 24 hours after VFI administration for safety, PK, and PD assessments. Subjects will return to the CRU for an end-of-study (EOS) visit on Day 21 (± 1 day).

Cohort 2:

Eligible subjects will receive a dose of VFI followed 160 minutes later by a single dose of Iohexol on Day 1 and a second dose of VFI 24 hours following the initial dose of VFI. Subjects will remain resident in the CRU for at least 24 hours after the second VFI administration for safety, PK, and PD assessments. Subjects will return to the CRU for follow-up visits on Days 5 (± 1 day), 9 (± 1 day), and 16 (± 1 day) and an EOS visit on Day 22 (± 1 day).

Cohorts 3 and 4:

Eligible patients will receive a single dose of VFI followed 160 minutes later by a single dose of Iohexol on Day 1.

Patients enrolled into Cohort 3 at ICON Early Phase Services will remain resident in the CRU for at least 24 hours after VFI administration for safety, PK, and PD assessments. Patients will return to the CRU for follow-up visits on Days 4 (± 1 day), 8 (± 1 day), and 15 (± 1 day), and an EOS visit on Day 21 (± 1 day).

Patients enrolled into Cohorts 3 or 4 at UAB will remain in the CRU through the 12-hour sample collection after VFI administration for safety, PK, and PD assessments. Patients will stay at a local hotel near the CRU and will return to the CRU on Day 2 for 24-hour sample collection. Patients will return to the CRU for follow-up visits on Days 4 (± 1 day), 8 (± 1 day), and 15 (± 1 day), and an EOS visit on Day 21 (± 1 day).

Refer to [Table 2.1](#), [Table 2.2](#), and [Table 2.3](#) for the Schedules of Assessments and Procedures.

CONFIDENTIAL

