10.1.11.4 Vital Signs

Vital signs data including pulse oximetry will be listed by subject at each visit and time point. Absolute and change from baseline vital signs values will be summarized by cohort at each visit and time point. Any unscheduled measurements will only be displayed in the listings.

Clinical significance will be indicated in the data listing. Out of range vital signs values will be flagged in the data listing.

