10.1.11.5 Electrocardiograms

Electrocardiogram data will be listed by subject at each visit and time point.

Observed value and change from baseline of ECG parameters (HR, RR, PR, QRS, and QT and QT interval corrected for HR using Fridericia's formula (QTcF) intervals) will be summarized by cohort at each nominal timepoint. Any unscheduled measurements will only be displayed in the listings. Clinical significance will be indicated in the data listing.

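### The early-recording allowance has no floor at dosing: the 15-minute ECG may be taken at the VFI bolus and the 170-minute vital signs at the nominal iohexol injection time, and the SAP has no actual-time rule

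*Protocol*

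**What the plan says.** Protocol Tables 2.1, 2.2, 2.3.1 and 2.3.2 carry the same note, repeated under SAP Tables 1.1 to 1.3. It applies "In the event that multiple postdose procedures are required to be conducted at the same nominal time point". It puts the ECG first, vital signs second and the blood draw third, and adds that "Electrocardiograms and vital signs may be conducted up to 15 and 10 minutes, respectively, prior to the nominal time". The stated purpose is "to minimize the potential autonomic effects of blood draws on these measurements". The note sets no minimum interval after dosing.

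The column times are defined as "Nominal Time Relative to Start of VFI Bolus Injection". The ECG rows show a predose reading, one at 15 min, and nothing more until 12 h or later. Column shifts in the extracted tables make it unclear whether that last mark sits at 12 h or 24 h.

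For Cohorts 3 and 4, Protocol 5.1 states: "Eligible patients will receive a single dose of VFI followed 160 minutes later by a single dose of Iohexol on Day 1". Cohort 2 has the same Day 1 interval. Vital signs in these cohorts are scheduled at 160 and 170 min, and next at 280 min. In Cohort 1, the albumin infusion runs from 130 to 160 min (Table 2.4), with vital signs at 165 min.

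Under SAP 10.1.11.5, ECG values and changes from baseline "will be summarized by cohort at each nominal timepoint". Under SAP 10.1.11.4, "Absolute and change from baseline vital signs values will be summarized by cohort at each visit and time point". Actual times are specified for the PK parameters (SAP 9.1.1). No corresponding rule exists for ECGs or vital signs.

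**The concern.** ECGs and vital signs are listed among the primary safety endpoints (Protocol 10.3.1.1). A scheduled postdose reading tells us about an acute effect only if it is taken after the agent has been given. At two points the early allowance is exactly as long as the interval since the injection, so a fully compliant reading can have no exposure behind it. Summarised under its nominal time, it pulls the cohort's mean change from baseline towards zero.

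The ECG matters more, because no other scheduled ECG falls between dosing and 12 h or later. For iohexol, a reading at 160 min repeats one already scheduled at injection, and the first hour and more after the injection then has no scheduled vital signs.

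**Working it through.** **Inputs.** Early allowance: 15 min for ECGs, 10 min for vital signs (the note). VFI bolus at 0 min. Iohexol at 160 min. Albumin from 130 to 160 min (Table 2.4). Nominal times from the schedules of assessments.

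**Does the note apply at these times?** Yes. At 15 min an ECG, vital signs and a blood sample coincide. At 170 min vital signs coincide with VFI and iohexol samples. At 165 min in Cohort 1 vital signs coincide with a blood sample.

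**The plan's own mapping (Table 2.5).** Time after iohexol = nominal time − 160:
- 170 − 160 = 10 min, as stated.
- 280, 310, 340, 370, 480 and 720 min give 120, 150, 180, 210, 320 and 560 min, as stated.

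**Earliest permitted reading = nominal time − allowance.**

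| Reading | Earliest time | Relative to the event it follows |
|---|---|---|
| 15-min ECG | 15 − 15 = 0 min | 0 min after the start of the VFI bolus |
| 15-min vital signs | 15 − 10 = 5 min | 5 min after VFI |
| 170-min vital signs (Cohorts 2–4, Day 1) | 170 − 10 = 160 min | 0 min after nominal iohexol |
| 280-min vital signs (same) | 280 − 10 = 270 min | 110 min after iohexol |
| 165-min vital signs (Cohort 1) | 165 − 10 = 155 min | 5 min before the albumin ends |

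If the 170-min reading is taken at 160 min, the next vital signs fall 110 to 120 min after iohexol (270 − 160 and 280 − 160).

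**Effect on a summary.** Assume a full cohort of 8, a true acute mean change d in subjects read after exposure, and an expected change of zero in k subjects read at injection. The expected cohort mean change is d × (1 − k/8). One such reading removes 1/8 = 12.5% of the effect, four remove 50%, and eight remove all of it. The documents do not say how often k would exceed zero.

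**Ceilings.** The ECG issue could touch at most 4 × 8 = 32 subjects, and the iohexol issue at most 3 × 8 = 24.

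**Allowance that removes the overlap.** It must be under 15 min for the 15-min ECG, under 170 − 160 = 10 min for the 170-min vital signs, and under 165 − 160 = 5 min for the 165-min vital signs.

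**The case against.** The best defence is that the window is permissive, has a sound reason, and refers to postdose procedures, so sites would understand that the reading follows the dose. The study is descriptive and has no hypotheses. The first-in-human study reported no clinically relevant ECG or vital-sign effects at VFI doses up to 150 mg, against 47 mg here. All of this lowers the priority. It does not close the gap: the word postdose sets no minimum interval, and the recommended order, with blood samples held to ±1 min at these times, favours recording the ECG and vital signs early.

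Several stronger readings are tempting but not supported:
- **The 170-min vital signs may precede iohexol.** The allowance reaches the nominal injection time and stops there. A reading before the injection would need iohexol to be given late, which is a separate matter.
- **The pre/post-iohexol split is the only separation of agents.** Cohort 2 on Day 2 and all of Cohort 1 provide VFI readings with no iohexol injection that day. Protocol 10.6 also plans summaries by treatment, and vital signs from 280 min onward are post-iohexol under any permitted timing.
- **Detection of anaphylaxis is compromised.** The risk that the protocol names is a dextran reaction to VFI. VFI vital signs can be no earlier than 5, 20 and 50 min at the 15-, 30- and 60-min points. Close monitoring, adverse event collection and unscheduled ECGs also apply.
- **The albumin reading has no exposure.** At 155 min, 25 of the 30 infusion minutes have passed, and later readings at 195 and 205 min follow the infusion. This is a lesser point.
- **The SAP labels these readings postdose.** It does not use that label. The inference is direct for ECGs, which are summarised by nominal time, and reasonable for vital signs.

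**Conclusion.** The point holds in a limited form. The schedules permit one ECG reading (15 min, all cohorts) and one vital-sign reading (170 min, Cohorts 2 to 4, Day 1) to be taken at the injection they are meant to follow. The SAP would still summarise them at their nominal time. A third reading, the Cohort 1 vital signs at 165 min, may fall up to 5 min before the albumin infusion ends.

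The counts of 32 and 24 subjects are ceilings. They require full cohorts and every reading at the outer minute of the window, so they are not an expected effect. No likely timing distribution can be drawn from the documents, and the actual dilution therefore cannot be estimated. The conclusion rests on the note being applied as written and on iohexol being given at its nominal time. Priority is low to moderate: the rule can produce a wrong summary and is cheap to correct.

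**What to change.** **Protocol.** Amend the note under Tables 2.1, 2.2, 2.3.1 and 2.3.2, and its copies under SAP Tables 1.1 to 1.3. The early allowance should not be able to move a postdose reading to or before the dose, or the end of the infusion, that it follows. Set a shorter allowance for the 15-min ECG and for the 165- and 170-min vital signs, within the limits derived above. The documents give no basis for a particular length. The sponsor should choose one that fits the sequence of ECG, vital signs and blood draw, including the 5-minute rest beforehand.

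**SAP 10.1.11.4 and 10.1.11.5.** Add a sentence classifying each reading as pre- or postdose by its actual time relative to the agent concerned. Any reading taken at or before the dose should be listed but left out of the postdose time-point summary.

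**Cost.** A table-note amendment and one SAP sentence, with no added procedures. A few readings will fall closer to a blood draw, which gives up a little of the protection the window was meant to provide, and the 15-min sequence becomes tighter for site staff.

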**Table 2.3.1 UAB Schedule of Assessments and Procedures – Cohorts 3 and 4 (Single-dose Administration of VFI)**

Study Procedure	Screening	Treatment Period															Discharge		Follow-up			EOS b
		1															2		4 (± 1)	8 (± 1)	15 (± 1)	21 (± 1)
Study Day	-21 to -1	Pre (UAB)	0	15	30	60	120	160	170	280	310	340	370	480	12	24	32	72	168	336	480	
Nominal Time Relative to Start of VFI Bolus Injection			m	m	m	m	m	m	m	m	m	m	m	m	h	h	h	h	h	h	h	
Informed consent	X																					
Inclusion/exclusion criteria	X	X a																				
In House Residency		X	X	X	X	X	X	X	X	X	X	X	X	X	X	X						
Demographics	X																					
Height	X																					
Body weight	X	X a																				X
BMI c	X	X a																				
Medical and surgical history	X	X a,d																				
Physical examination	X	X a															X					X
Vital signs and pulse oximetry e	X	X	X	X	X	X		X	X	X	X	X	X	X	X	X	X	X	X	X	X	X
12-lead ECG e	X	X a		X													X					
Clinical laboratory tests f	X	X a														X g	X		X g	X g	X g	X
Renal function assessment h	X	X a																				

CONFIDENTIAL

**Table 2.3.1 UAB Schedule of Assessments and Procedures – Cohorts 3 and 4 (Single-dose Administration of VFI)**

Study Procedure	Screening	Treatment Period															Discharge		Follow-up			EOS b
		1															2		4 (± 1)	8 (± 1)	15 (± 1)	21 (± 1)
Study Day	-21 to -1	Pre (UAB)	0	15	30	60	120	160	170	280	310	340	370	480	12	24	32	72	168	336	480	
Nominal Time Relative to Start of VFI Bolus Injection			m	m	m	m	m	m	m	m	m	m	m	m	h	h	h	h	h	h	h	
Urine protein to creatinine ratio i		X															X					
Serology (HIV, HBsAg, HCV)	X																					
FSH (females only)	X																					
Pregnancy Test (females only)	X	X																				
Urine drugs of abuse and serum alcohol screen	X	X a																				
In-house residency		X	X	X	X	X	X	X	X	X	X	X	X	X	X							
FAST VFI administration			X																			
Iohexol administration								X														
FD001 and FD003 PK/PD plasma samples			Refer to Table 2.6 for the PK and PD sampling schedule.																			

CONFIDENTIAL

